6.2 Multiplicity Adjustment

No multiplicity adjustment is required for this bioequivalence study.

6.3 Statistical Analysis

6.3.1 General considerations

The pharmacokinetic parameters will be analyzed to evaluate the differences between the test and reference study interventions by applying referenced scaled average bioequivalence approach. This approach will be assessed based on GMR and 90% confidence interval for ln-transformed PK parameters Cmax and AUCt using RSABE.

All the statistical analysis will be performed using SAS® Version 9.4 or higher (SAS Institute Inc., USA).

The participants having pharmacokinetic parameters available for 2 reference treatments will be included for calculation of intra-subject variability of reference study intervention.

Descriptive statistics & average bioequivalence analysis will be performed on the participants having pharmacokinetic parameters available for at least 1 test and 1 reference arm.

6.3.2 Primary Endpoint(s)/Estimand(s) Analysis

6.3.2.1 Descriptive statistics

Statistical analysis for primary endpoints will include descriptive statistics for the following pharmacokinetic parameters:

Cmax and AUC(0-t)

Descriptive statistics (N, n, arithmetic mean, 95% CI of arithmetic mean, geometric mean, 95% CI of geometric mean, SD, median, minimum and maximum) will be presented for primary PK parameters.

Average values of Test Study Intervention-T and Reference Study Intervention-R for PK parameters for each participant will be calculated and reported. Descriptive statistics will be calculated and reported for the same data.

Individual values of PK parameters for Test Study Intervention-T (first administration), Test Study Intervention-T (second administration), Reference Study Intervention-R (first administration) and Reference Study Intervention-R (second administration) for each participant will be calculated and reported. Descriptive statistics will be calculated and reported for the same data.

Version 00

PK parameters will be analyzed to evaluate the differences between the test and reference products by applying SCABE following EMA guidelines in investigation of bioequivalence regarding highly variable drug product (% of CVw >30), otherwise ABE will be applied.

6.3.2.2 Analysis of Variance (ANOVA)

Analysis of Variance (ANOVA) will be used on ln-transformed pharmacokinetic parameters Cmax and AUC(0-t) for albendazole or albendazole sulfoxide. The ANOVA model will include sequence, participant(sequence), period and formulation as fixed effects.

Each analysis of variance will include calculation of ratio of geometric least-squares means and the standard error associated with these ratios.

The above statistical analyses will be done using PROC GLM of SAS® procedure. A significance level of 5% (alpha =0.05) will be used for the model.

6.3.2.3 90% Confidence Interval

90% confidence intervals for the ratio of geometric least squares means between drug formulations will be calculated for ln-transformed data of Cmax and AUC(0-t) for albendazole and albendazole sulfoxide.

6.3.2.4 Ratio analysis

Ratio of geometric least squares means of test and reference formulations will be computed and reported for ln-transformed pharmacokinetic parameters Cmax and AUC(0-t) for albendazole and albendazole sulfoxide.

6.3.2.5 Intra-subject variability

Intra-subject variability of reference study intervention-R will be computed and reported for Intransformed pharmacokinetic parameters Cmax and AUC(0-t) for albendazole and albendazole sulfoxide.

The existence of outlier subjects that inflate the intra-subject variability will be assessed. In case of such outliers, results will be reported with and without those outliers.

6.3.2.6 Missing and non-reportable values

If 1 or more NQ values occur in a profile before the first measurable concentration, they will be assigned a value of zero concentration.

If a single NQ value occurs between measurable concentrations in a profile, the NQ should be omitted (set to missing) in the derivation of pharmacokinetic parameters and statistical analysis.

If 2 or more NQ values occur in succession between measurable concentrations, the values in question will be set to missing. For the derivation of pharmacokinetic parameters, these NQs will be omitted. The NQ values will be set to 0 and the trapezoidal rule will be applied to all the observed data.

NQs which occur after the last measurable concentration will be omitted (set to missing) in the derivation of pharmacokinetic parameters and statistical analysis. Any missing samples (M) concentration value will be disregarded in pharmacokinetic and statistical analysis.

6.3.2.7 Intercurrent event and handling of missing data

The data will be affected by occurrence of the intercurrent event and only data available while the participant is receiving the treatment will be used under while-on treatment policy strategy. Participant level missing data will not be imputed, and available data will be used in the analysis.

In the case of emesis/vomiting or use of prohibited/rescue medication, the data for that period will not be used for the analysis of PK parameters relating to the primary endpoint using hypothetical strategy.

6.3.2.8 Bioequivalence criteria

Based on the statistical results of 90% confidence interval for the ratio of the geometric least square means for both ln-transformed pharmacokinetic parameters Cmax and AUC(0-t), conclusion will be drawn for Test Study Intervention-T vs. Reference Study Intervention-R for albendazole with following considerations.

For Cmax and AUC(0-t):

- 1. If within-reference intra-subject CV of ln-transformed Cmax and/or AUC(0-t) \leq 30% then bioequivalence of the test study intervention with that of the reference study intervention will be concluded, if the 90% confidence interval falls within the acceptance range of 80.00–125.00% for ln-transformed pharmacokinetic parameter Cmax and AUC(0-t).
- 2. If within-reference intra-subject CV of ln-transformed Cmax and/or AUC(0-t) > 30% then Cmax and/or AUC(0-t) limit will be widened using scaled-average-bioequivalence. Under scaled-average-bioequivalence, [U,L] = exp [$\pm k \cdot _{SWR}$] where U is the upper limit of the acceptance range, L is the lower limit of the acceptance range, k is the regulatory constant set to 0.760 and S_{WR} is the within-subject standard deviation of the ln transformed values of Cmax and/or AUC(0-t) of the reference study intervention.
- 3. If within-reference intra-subject CV of ln-transformed Cmax and/or AUC(0-t) \geq 50% then Cmax and/or AUC(0-t) bioequivalence limits will be widened to a maximum of 69.84 143.19%.

Bioequivalence of the test study intervention with that of the reference study intervention will be concluded for Cmax and AUC(0-t), if both of the following conditions are satisfied:

- The 90% confidence interval for ln-transformed data of Cmax and AUC(0-t) falls within the respective newly widen range [U, L] = $\exp\left[\pm k \cdot _{SWR}\right]$, which is based upon the within-subject variability observed for respective pharmacokinetic parameter.
- The geometric least square mean ratio (GMR) of test to reference for Cmax and AUC(0-t) falls within the acceptance range of 80.00–125.00%.

Data of metabolite albendazole sulfoxide will be provided as supportive information only.

6.3.3 Secondary Endpoint(s)/Estimand(s) Analysis

Statistical analysis for secondary endpoints will include descriptive statistics for the following pharmacokinetic parameters:

Albendazole: AUC0-∞, Tmax, t1/2, λz and AUC %Extrap obs

Albendazole sulfoxide: AUC0-∞, AUC0-t, Cmax, Tmax, t1/2, λz and AUC %Extrap obs.

Descriptive statistics (N, n, arithmetic mean, 95% CI of arithmetic mean, SD, median, minimum, maximum and geometric mean with 95% CI) will be presented for untransformed secondary PK parameters.

Average values of Test Study Intervention-T and Reference Study Intervention-R for PK parameters for each participant will be calculated and reported. Descriptive statistics will be calculated and reported for the same data.

Individual values of PK parameters for Test Study Intervention-T (first administration), Test Study Intervention-T (second administration), Reference Study Intervention-R (first administration) and Reference Study Intervention-R (second administration) for each participant will be calculated and reported. Descriptive statistics will be calculated and reported for the same data.

In case of treatment discontinuation due to any reason, only the data available before the occurrence of intercurrent event will be used to estimate secondary PK parameters using while-on-treatment policy strategy.

If any participant experience emesis/vomiting or if a prohibited/rescue medication is used by any participant, the participant's data for that period will not be used for the analysis of secondary endpoints related to PK using hypothetical strategy.

Treatment policy strategy will be used to analyze the secondary endpoints related to safety to make use of all available data for a participant.

7 Safety Assessment and Analysis

7.1 Safety Assessment

Demographic data

Demographic data such as date of birth, sex, race, age, and ethnicity will be assessed on screening visit.

Body Measurement

Body measurement data such as height, weight and BMI will be assessed on screening visit.

Medication history

Current medication (prescribed medication & OTC medication, herbal remedies, cimetidine, praziquantel, dexamethasone, ritonavir, phenytoin, carbamazepine, phenobarbital) and usage of any concomitant therapy or any ingestion of medicine in the previous 14 days prior to dosing of period I and any vaccine (including COVID-19 vaccine) from 14 days prior to dosing of period I. Medication history will be recorded on PERIOD 1 (Day 1)

Physical examination

Physical examination will be assessed on screening visit, check in (Day 1) and check-out (Day 2) of each period.

Urine drug scan and breath alcohol test

Drug abuse in urine and Breath alcohol test will be performed on check-in of each period.

Chest X-ray

Chest X-ray (within the last 6 months) (postero-anterior view) will be carried out at the time of screening.

Vital signs

Vitals (sitting blood pressure and radial pulse) will be recorded at pre-dose (within 60 minutes before the dosing) and at 2, 4, 6, 12 and 24 hours post-dose in each period.

Note: All post-dose vitals will be performed within \pm 40 minutes of the scheduled time.

Recording of vital signs (blood pressure, respiratory rate and radial pulse and body temperature) will be done at screening, after check-in, before check-out in each period.

Note: Vital signs before checkout may be started 120 minutes prior to the scheduled time of checkout of each participant.

12-lead ECG

12-lead ECG will be carried out at the time of screening (up to 28 days before Dosing in period I).

Clinical safety laboratory tests

Serology tests (HIV AB (1 & 2), Anti HCV and HBsAg) will be performed at the time of screening. Urine parameters will be performed at the time of screening.

Urine parameters: Specific Gravity, Leucocytes, Bilirubin, Urobilinogen, Erythrocytes, pH, Protein, Ketones, Glucose, Nitrite, Microscopic examination (As applicable).

Laboratory assessment for hematology and biochemistry will be performed at the time of screening. Laboratory assessment for hematology and biochemistry (except random glucose, sodium, potassium, chloride, alkaline phosphatase) will be performed at the end of the study (at the time of check-out of period IV).

Laboratory assessment for liver function test (SGPT, SGOP and total bilirubin) will be performed prior to check-in of period II, III and IV.

Hematology: Hemoglobin [Hb], RBC count, HCT, MCV, MCH, MCHC, RDW CV, Platelet count, WBC (total), Neutrophils %, Lymphocytes %, Eosinophils %, Monocytes %, Basophils %, Neutrophils abs, Eosinophils abs

Biochemistry: Random Glucose, Bilirubin Total, Total Protein, Albumin, Serum Globulin, A/G ratio, SGOT (AST), SGPT (ALT), Creatinine, Blood Urea Nitrogen, Sodium, Potassium, Chloride, Alkaline phosphatase.

Pregnancy testing

Serum Pregnancy test for female participants will be done at the time of screening, prior to checkin of each period and at the end of the study (at the time of check-out of period IV). Pregnancy testing must be done even if the participant is menstruating at the time of the study visit. The study intervention may only be administered if the pregnancy test is negative.

7.2 Safety Analysis

Safety analysis will be done on the safety set. Safety variables include AEs, clinical laboratory parameters, vital signs, physical examinations. Safety variables will be listed and summarized with descriptive statistics as appropriate.

Continuous variables will be Summarized by treatment/sequence group using summary statistics (number of observations, mean, standard deviation, median, minimum and maximum etc.) as applicable. Categorical values will be summarized by the treatment group using frequencies and percentages.

Result obtained when evaluating safety (adverse events, vital signs, clinical laboratory tests etc.) will be listed and evaluated descriptively.

Adverse events

All AEs reported during the study must be included in the safety analysis. AEs will be classified by system organ class, by preferred term from the MedDRA version 25.0 or higher. They will be presented in individual listings and summary tables, and evaluated descriptively and in terms of

frequencies, by treatment. As will be summarized for all subjects in Safety set across two treatment groups by System Organ Class (SOC) and Preferred Term (PT). p-value using chi-square test or fisher exact test will be provided for the AE data.

Intensity refers to the severity of the AE.: Mild, Moderate, Severe.

Clinical laboratory values

LAMBDA

Clinical laboratory values will be compared to their reference ranges. Values outside the normal ranges will be highlighted. The Investigator has to comment, whether the abnormality is clinically relevant.

Other safety parameters

All results of vital sign measurements will be presented in individual listings. Where appropriate, results and possible changes in parameters will be evaluated descriptively or by descriptive statistics (mean, SD, median, range). Descriptive statistics (N, n, mean, SD, median, minimum and maximum) will be presented for absolute and change from baseline values of vital signs parameters at each timepoint.

Demographic data will be shown in tables as mean values, SD and ranges (min, max).

Clinical laboratory data will be shown in tables as mean values, SD and ranges (min, max) as applicable.

Physical examination, 12 lead ECG, Chest X-Ray performance and concomitant medication will be presented in data listings.

Protocol deviations

A list of all protocol deviations and an assessment of their impact will be included in listing. The deviations will include dosing related, IMP related, lab related, early, late or missed safety assessments, etc.

A number of participants with minor and major deviations will be provided.

8 Change from the protocol

"The ANOVA model will include sequence, participant(sequence), period and formulation as fixed effects" as per the WHO requirements.

9 Interim analysis

No interim analysis has been planned in this study.

[figure not shown]
10 Software Information for Analysis

SAS® Version 9.4 or higher (SAS Institute Inc., USA) will be used for statistical and safety analysis.

Phoenix® WinNonlin® Version 8.3 or higher (Certara L.P.) will be used for pharmacokinetic analysis.

11 Format Specifications for outputs

1. Output files of SAS procedures/Phoenix WinNonlin (statistical analyses, summary tables, individual data listings, etc.) will be produced as PDF files.

Project No. 0110-23 Version 00

- 2. Each individual PDF file will contain the statistical analysis output, i.e. a summary table, or data listing grouped by treatment or/and visit, for one analysis population, and for a single type of analysis.
- 3. The rules for grouping may vary according to the type of data (study outcome, safety), individual data listings, listings of derived variables, etc. and the type of output file which is produced (statistical analyses, summary tables, graphs).
- 4. Page format will be "A4".
- 5. Each listing will be numbered in the format Page X of Y (where Y denotes total number of pages in that particular listing). Page number will appear in the bottom right part of the listing.
- 6. For each output, 'Lambda Therapeutic Research Ltd.' Will appear in the Top left corner of the Header, 'Confidential' and 'Title' of the output will appear in the Centre of the Header and towards the Top right corner the 'project number' will be presented.
- 7. The font and font size for header/footer and body of the output will be Courier New size 9 pt which will be generated from SAS. The font and font size for header/footer and body of the output will be Times New Roman 12 pt which will be generated from Phoenix WinNonlin.

12 List of Tables

14.1	Demographic data
14.1.1	Demographic data and baseline characteristics (Randomized set)
14.1.2	Demographic data and baseline characteristics (Safety set)
14.1.3	Demographic data and baseline characteristics (PK set)
14.1.4	Visit wise distribution of subjects (Randomized set)
14.1.5	Visit wise distribution of subjects (Safety set)
14.1.6	Visit wise distribution of subjects (PK set)
14.1.7	Summary of protocol deviations
14.2	Pharmacokinetic data
14.2.1	Plasma albendazole data
14.2.1.1	Summary statistics of pharmacokinetic parameters for albendazole
14.2.1.2	Pharmacokinetic parameters (untransformed) of albendazole for Test Product-T and Reference Product-R
14.2.1.3	Individual pharmacokinetic parameters (untransformed) of albendazole for Test Product-T1 (first administration), Test Product-T2 (second administration), Reference Product-R1 (first administration) and Reference Product-R2 (second administration)
14.2.1.4	Pharmacokinetic parameters (untransformed) of data excluded from statistical analysis for albendazole (if applicable)
14.2.1.5	Pharmacokinetic parameters (ln-transformed) of albendazole for Test Product-T and Reference Product-R
14.2.1.6	Individual pharmacokinetic parameters (In-transformed) of albendazole for Test Product-T1 (first administration), Test Product-T2 (second administration), Reference Product-R1 (first administration) and Reference Product-R2 (second administration)
14.2.1.7	Plasma concentration of albendazole for Test Product-T1 (first administration)
14.2.1.8	Plasma concentration of albendazole for Test Product-T2 (second administration)
14.2.1.9	Plasma concentration of albendazole for Reference Product-R1 (first administration)
14.2.1.10	Plasma concentration of albendazole for Reference Product-R2 (second administration)
14.2.1.11	Plasma concentration of data excluded from statistical analysis for albendazole (if applicable)
14.2.2	Plasma albendazole sulfoxide data
14.2.2.1 14.2.2.2	Summary statistics of pharmacokinetic parameters for albendazole sulfoxide Pharmacokinetic parameters (untransformed) of albendazole sulfoxide for Test
14.2.2.3	Product-T and Reference Product-R Individual pharmacokinetic parameters (untransformed) of albendazole sulfoxide for Test Product-T1 (first administration), Test Product-T2 (second administration), Reference Product-R1 (first administration) and Reference Product-R2 (second administration)

14.2.2.4	Pharmacokinetic parameters (untransformed) of data excluded from statistical analysis for albendazole sulfoxide (if applicable)
14.2.2.5	Pharmacokinetic parameters (In-transformed) of albendazole sulfoxide for Test Product-T and Reference Product-R
14.2.2.6	Individual pharmacokinetic parameters (ln-transformed) of albendazole sulfoxide for Test Product-T1 (first administration), Test Product-T2 (second administration), Reference Product-R1 (first administration) and Reference Product-R2 (second administration)
14.2.2.7	Plasma concentration of albendazole sulfoxide for Test Product-T1 (first administration)
14.2.2.8	Plasma concentration of albendazole sulfoxide for Test Product-T2 (second administration)
14.2.2.9	Plasma concentration of albendazole sulfoxide for Reference Product-R1 (first administration)
14.2.2.10	Plasma concentration of albendazole sulfoxide for Reference Product-R2 (second administration)
14.2.2.11	Plasma concentration of data excluded from statistical analysis for albendazole sulfoxide (if applicable)
14.2.3	Actual time points used for pharmacokinetic evaluation
14.3	Safety data
14.3.1	Overall summary of treatment emergent adverse events (Safety set)
14.3.2	Summary of treatment emergent adverse events by system organ class and preferred term (Safety set)
14.3.3	Summary of treatment emergent adverse events by relationship to study drug and system organ class and preferred term (Safety set)
14.3.4	Summary of treatment emergent adverse events by severity grade and system organ class and preferred term (Safety set)
14.3.5	Summary of subject disposition
14.3.6	Summary of vital signs (Safety set)
14.3.7	Summary of change from baseline for vital signs (Safety set)
14.3.8	Summary of quantitative safety laboratory variables (Safety set)
14.3.9	Summary of qualitative safety laboratory variables (Safety set)
14.3.10	Summary of concomitant medication (Safety set)

13 List of Listings

16.2.1	Subject disposition
16.2.1.1	Screen failure subjects
16.2.1.2	Study completion status
16.2.1.3	Subject distribution in analysis population
16.2.1.4	Inclusion - Exclusion criteria

Lambda Therapeutic Research Ltd. Statistical Analysis Plan (SAP)

Albendazole Tablets IP 400 mg

Version 00

16.2.1.5	Inclusion criteria description
16.2.1.6	Exclusion criteria description
16.2.2	Protocol deviations
16.2.3	Subjects excluded from the analysis
16.2.3.1	Subjects excluded from the analysis (PK set)
16.2.4	Demographic data
16.2.4.1	Demographic data and baseline characteristics
16.2.4.2	Personal history
16.2.4.3	Medical and surgical history details
16.2.4.4	Physical examination
16.2.4.5	Medication history
16.2.5	Compliance and/or drug concentration data
16.2.5.1	Study drug administration
16.2.5.2	Compliance assessment
16.2.5.3	PK Sample collection
16.2.5.4	Concentration-time data for albendazole
16.2.5.5	Pharmacokinetic data for albendazole
16.2.5.6	Concentration-time data for albendazole sulfoxide
16.2.5.7	Pharmacokinetic data for albendazole sulfoxide
16.2.7	Adverse events (each subject)
16.2.7.1	Adverse events by severity, relationship to the study drug and by MedDRA term
16.2.7.2	Serious adverse events (if applicable)
16.2.8	Listing of individual laboratory measurements (by Subject)
16.2.8.1	Central laboratory tests
16.2.8.2	Safety laboratory analysis
16.2.9	Individual subject data listings
16.2.9.1	12 Lead electrocardiogram
16.2.9.2	Chest x-ray
16.2.9.3	Body measurements
16.2.9.4	Vital signs
16.2.9.5	Urine drug scan and breath alcohol test
16.2.9.6	Lifestyle compliance assessment
16.2.9.7	Subjects date of visit
16.2.9.8	Unscheduled visit (if applicable)
16.2.10	Prior - concomitant medication
14 List of Figures	
14.2.4	Figures of pharmacokinetic data

14.2.4.1	Mean plasma concentration vs. time curve for albendazole (Linear and Semi-
	log Plot)
14.2.4.2	Combined mean plasma concentration vs. time curve for albendazole (Linear and Semi-log Plot)
14.2.4.3	Mean (± SD) plasma concentration vs. time curve for albendazole (Linear and Semi-log Plot)
14.2.4.4	Median plasma concentration vs. time curve for albendazole (Linear and Semi-log Plot)
14.2.4.5	Median (range) plasma concentration vs. time curve for albendazole (Linear and Semi-log Plot)
14.2.4.6	Summary plot of individual plasma concentration vs time for albendazole (Linear and Semi-log Plot)
14.2.4.7	Mean plasma concentration vs. time curve for albendazole sulfoxide (Linear and Semi-log Plot)
14.2.4.8	Combined mean plasma concentration vs. time curve for albendazole sulfoxide (Linear and Semi-log Plot)
14.2.4.9	Mean (± SD) plasma concentration vs. time curve for albendazole sulfoxide (Linear and Semi-log Plot)
14.2.4.10	Median plasma concentration vs. time curve for albendazole sulfoxide (Linear and Semi-log Plot)
14.2.4.11	Median (range) plasma concentration vs. time curve for albendazole sulfoxide (Linear and Semi-log Plot)
14.2.4.12	Summary plot of individual plasma concentration vs time for albendazole sulfoxide (Linear and Semi-log Plot)
16.2.6	Individual pharmacokinetic response data
16.2.6.1	Individual plasma concentration vs. time curve for albendazole (Linear and Semilog Plot)

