SGOT	:	Serum glutamic-oxaloacetic transaminase
SGPT	:	Serum glutamic pyruvic transaminase
SCABE	:	Scaled average bioequivalence
SOC	:	System organ class
SWR	:	Within-subject standard deviation of the reference study intervention
t1/2	:	Terminal half-life
TOST	:	Two one-sided t-test
Tmax	:	Time of the maximum measured plasma concentration
WBC	:	White blood cell
WHO	:	World health organization

1 Introduction

This statistical analysis plan provides the framework for the analysis and summarization of the data generated from the study conducted to assess the bioequivalence Albendazole Tablets IP 400 mg (Test) of Biddle Sawyer Limited (GSK group company) compared with Albendazole Tablets 400 mg (Reference) of Glaxo SmithKline Consumer Healthcare, South Africa (PTY) Ltd in Healthy, Adult Participants under Fed Condition.

2 Objective, Endpoints and Estimands

Objectives	Endpoints
Primary	
To evaluate if Test Study Intervention (T): Albendazole tablets IP 400 mg, manufactured by Biddle Sawyer Limited is bioequivalent to Reference Study Intervention (R): Albendazole Tablets 400 mg, manufactured by GSK Consumer Healthcare, South Africa (PTY)	Albendazole Cmax and AUC(0-t)
Secondary	
To assess secondary pharmacokinetic parameters of Test Study Intervention (T): Albendazole tablets IP 400 mg relative to Reference Study Intervention (R): Albendazole tablets 400 mg.	 Albendazole AUC0-∞, Tmax, t1/2, lambda-z (λz) and AUC_%Extrap_obs. Albendazole sulfoxide Cmax, AUC(0-t), AUC0-∞, Tmax, t1/2, lambda-z (λz) and AUC_%Extrap_obs.
To assess the safety and tolerability of a single oral dose of the test versus the reference study intervention.	 Incidence of AE. Absolute and change from baseline in vital signs parameters at each timepoint.

Primary estimand/coprimary estimands:

The primary clinical question of interest is:

To evaluate if Test Study Intervention (T): Albendazole tablets IP 400 mg is bioequivalent to Reference Study Intervention (R) Albendazole tablets 400 mg in healthy adult participants under fed conditions.

The estimand is described by the following attributes:

- **Population**: Healthy adult participants between 18 to 45 years of age.
- **Treatment condition**: Single dose of Albendazole tablets IP 400 or Albendazole tablets 400 mg, each treatment period given under fed conditions to healthy participants.
- Variable/endpoint: Cmax and AUC(0-t)

• Summary measure:

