Descriptive statistics (N, n, arithmetic mean, 95% CI of arithmetic mean, SD, median, minimum, maximum, and geometric mean) will be presented for untransformed secondary PK parameters (AUC0- ∞ , AUC(0-t), Tmax, t1/2, λ z and AUC_%Extrap_obs).

• Intercurrent events:

Same as primary endpoint

Rationale for estimand:

o The rationale of hypothetical strategy which is impacted to secondary PK parameters (AUC0-∞, AUC(0-t), Tmax, t1/2, λz and AUC_%Extrap_obs) during the study is same as primary estimands.

Secondary estimand(s) - 2(Safety)

The secondary clinical question of interest is:

To assess the safety and tolerability of a single oral dose of Test Study Intervention (T): Albendazole tablets IP 400 mg relative to Reference Study Intervention (R): Albendazole tablets 400 mg.

The estimand is described by the following attributes:

- **Population**: Healthy adult participants between 18 to 45 years of age.
- **Treatment condition**: Single dose of Albendazole tablets IP 400 mg or Albendazole tablets 400 mg, each treatment period given under fed conditions for healthy participants.
- Variable/endpoint: Incidence of AE and Absolute and change from baseline in vital signs parameters at each timepoint.

• Summary measure:

- o Number and percentage will be presented for incidence of AE.
- o Descriptive statistics (N, n, mean, SD, median, minimum, and maximum) will be presented for absolute and change from baseline values of vital signs parameters at each timepoint.

• Intercurrent events:

Permanent Treatment discontinuation due to any reason (includes COVID-19 positive, AE related withdrawal etc.) - Treatment policy strategy.

• Rationale for estimand:

Permanent Treatment discontinuation due to any reason will be handled with a treatment policy strategy as occurrence of AE until participant are on study will be collected and reported.

[figure not shown]
3 Overall Study Design

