14.3.6 Summary of vital signs (Safety set)

Lambda Therapeutic Research Ltd.

Confidential

Project No. 0110-23

Table 14.3.6

Summary of vital signs (Safety set)

Parameters (Unit)	Visit (Day)	Time Point	Statistics	TRTR (N=xx)	RTRT (N=xx)	Total (N=xx)	p-value
Pulse rate (beats/min)	Screening		n Mean (SD) Median Min, Max	xx xx.x (xx.xx) xx.x xx.x, xx.x	xx xx.x (xx.xx) xx.x xx.x, xx.x	xx xx.x (xx.xx) xx.x xx.x, xx.x	x.xxx
	Assessment Visit X	Time Point 1	n Mean (SD) Median Min, Max	xx xx.x (xx.xx) xx.x xx.x, xx.x	xx xx.x (xx.xx) xx.x xx.x, xx.x	xx xx.x (xx.xx) xx.x xx.x, xx.x	x.xxxx
		Time Point 2	n Mean (SD) Median Min, Max	xx xx.x (xx.xx) xx.x xx.x, xx.x	xx xx.x (xx.xx) xx.x xx.x, xx.x	xx xx.x (xx.xx) xx.x xx.x, xx.x	x.xxxx
	Assessment Visit Y	Time Point 1	n Mean (SD) Median Min, Max	xx xx.x (xx.xx) xx.x xx.x, xx.x	xx xx.x (xx.xx) xx.x xx.x, xx.x	xx xx.x (xx.xx) xx.x xx.x, xx.x	x.xxxx
Etc.	Etc.	Etc.	,	. ,	. ,	. ,	

N = Number of subjects in safety set, n = Number of subjects in respective categories

P-value is calculated using an independent t-test.

Treatment specification \rightarrow T = Test Product and R = Reference Product.

Reference Listing: 16.2.9.4

Output Generated on: DDMMMYYYY hh:mm

<Note for programmers: This table will continue for vital parameters like Systolic Blood Pressure (mmHg), Diastolic Blood Pressure (mmHg), Oral Body Temperature (°F), etc.>

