14.3.7 Summary of change from baseline for vital signs (Safety set)

Lambda Therapeutic Research Ltd.

Confidential

Project No. 0110-23

Table 14.3.7

Parameters	TT: '. (D.)	m:		TRTR	RTRT	Total
(Unit)	Visit (Day)	Time Point	Statistics	(N=xx)	(N=xx)	(N=xx)
Diastolic Blood Pressure (mmHg)	Assessment Visit X	Time Point 1	n	xx	xx	xx
			Mean (SD)	xx.x (xx.xx)	xx.x (xx.xx)	xx.x (xx.xx)
			Median	xx.x	XX.X	XX.X
			Min, Max	XX.X, XX.X	XX.X, XX.X	XX.X, XX.X
		Time Point 2	n	XX	XX	xx
			Mean (SD)	xx.x (xx.xx)	xx.x (xx.xx)	xx.x (xx.xx)
			Median	XX.X	XX.X	XX.X
			Min, Max	xx.x, xx.x	XX.X, XX.X	xx.x, xx.x
	Assessment Visit Y	Time Point 1	n	xx	xx	xx
			Mean (SD)	xx.x (xx.xx)	xx.x (xx.xx)	xx.x (xx.xx)
			Median	XX.X	XX.X	XX.X
			Min, Max	xx.x, xx.x	xx.x, xx.x	XX.X, XX.X
Etc.	Etc.	Etc.				

N = Number of subjects in safety set, n = Number of subjects in respective categories Change from Baseline (CFB) = Post Baseline assessment - Baseline assessment (0.00 Hrs Pre-Dose). Treatment specification -> T = Test Product and R = Reference Product. Reference Listing: 16.2.9.4

Project No. 0110-23

Lambda Therapeutic Research Ltd. Statistical Analysis Plan (SAP) Albendazole Tablets IP 400 mg

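### Vital signs are tabled by sequence only, so no planned output labels or pools this secondary safety endpoint by product

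*SAP*

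**What the plan says.** The objectives table in SAP section 2, matching Protocol section 3, states the second secondary objective as "To assess the safety and tolerability of a single oral dose of the test versus the reference study intervention". The safety estimand in SAP section 2 names the variable as "Incidence of AE and Absolute and change from baseline in vital signs parameters at each timepoint". Its treatment condition is a single dose of one product or the other, and its summary measure is descriptive statistics.

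For continuous safety data SAP 7.2 says "Continuous variables will be Summarized by treatment/sequence group using summary statistics", as applicable. Its sentence on vital signs says that descriptive statistics "will be presented for absolute and change from baseline values of vital signs parameters at each timepoint" and names no grouping.

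The shells are definite:

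- **14.3.6 (absolute values):** columns TRTR, RTRT, Total and p-value, with rows by visit and timepoint. The footnote reads "P-value is calculated using an independent t-test".
- **14.3.7 (change from baseline):** columns TRTR, RTRT and Total, with the same row structure. Change is defined as "Change from Baseline (CFB) = Post Baseline assessment - Baseline assessment (0.00 Hrs Pre-Dose"), without naming the period.
- **Listing 16.2.9.4:** sequence, visit and timepoint, but no treatment.

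The SAP's list of tables has no other vital-signs summary. Protocol 9.4.4 leaves the full description of the safety analyses to the SAP.

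**The concern.** The question is about products and the columns are about sequences. Each sequence receives both products, so a sequence column has a product meaning only within a single period, and that meaning reverses in the next one. The other endpoint of the same objective, adverse events, is tabled under Test and Reference headings in shells 14.3.1 to 14.3.4, and its listing (16.2.7.1) carries a treatment field. The two endpoints would therefore reach the study report on different groupings, with only one showing the contrast that the objective names.

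At stake is whether the report shows what post-dose vital signs looked like after Test and after Reference. The p-values in 14.3.6 could also be taken for product comparisons across the study, which they are not.

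**Working it through.** The plan gives no figure to reproduce. The check traces a product difference through the planned columns.

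**Inputs.** Sequences TRTR and RTRT with equal allocation (SAP 3.1, 3.4). Target 70 participants (SAP 3.3), so 35 per sequence if all complete. Vital signs at pre-dose and 2, 4, 6, 12 and 24 h in each period (SAP 7.1), so six scheduled timepoints per period. Period-specific visits are inferred from the visit labels in shell 14.1.4.

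**Step 1: what the columns show.** Let d be the true Test-minus-Reference difference after dosing, with no carryover. Set the Reference level to zero and ignore period effects, which cancel between columns.

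| Period | TRTR takes | RTRT takes | TRTR minus RTRT | Total |
|---|---|---|---|---|
| I | T | R | +d | d/2 |
| II | R | T | -d | d/2 |
| III | T | R | +d | d/2 |
| IV | R | T | -d | d/2 |

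The plain average of the four differences is (d - d + d - d)/4 = 0. Total is a half-and-half mixture of the products in every period.

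**Step 2: what can be recovered.** Each in-period cell holds one product, so four contrasts can be decoded. Let A1 to A4 be the TRTR means and B1 to B4 the RTRT means. With complete data, [(A1-B1) - (A2-B2) + (A3-B3) - (A4-B4)]/4 = (d + d + d + d)/4 = d, which is the crossover point estimate. Its within-participant standard error cannot be obtained from the table, because that needs the covariance between periods. With dropouts the match is only approximate.

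**Step 3: p-values.** For pulse, systolic and diastolic pressure alone, 14.3.6 would print 3 x 4 periods x 6 timepoints = 72 in-period p-values, none of which tests product across the study. Those at screening and at period I pre-dose compare groups that have had no drug.

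**Step 4: precision, as illustration only.** The documents give no SD or correlation for vital signs. Assume SD s and between-period correlation r, with all 70 participants complete.

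- One-period sequence contrast: SE = s x sqrt(2/35).
- Pooled within-participant contrast: SE = s x sqrt((1-r)/70).
- Ratio = 2/sqrt(1-r), so s cancels.

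With s = 10 mmHg and r = 0.5, the SEs are 10 x sqrt(2/35) = 2.39 and sqrt(50/70) = 0.85, a ratio of 2.8. The ratio is 2.2 at r = 0.2 and 4.5 at r = 0.8. It is already 2.0 at r = 0, so part of it reflects four periods against one and not the pairing.

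**The case against.** A reader might infer that the trial yields no Test or Reference estimate of vital signs, or that the safety objective goes unanswered for this endpoint. The documents do not support that. Rows are by visit and timepoint, the footnotes give the key to T and R, and each in-period cell is a summary for one product. Nor is the crossover information wholly lost, since step 2 recovers the point estimate under complete data. What is missing is labelling, pooling and a within-participant measure of precision.

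The SAP text also leaves room for product columns. The wording in 7.2 permits treatment as the grouping, and section 11 allows outputs grouped by treatment and lets the rules vary by type of data. This stands: the defect lies in the shells and the listing, not in the sentence of 7.2. It does not cure the defect, because the shells choose sequence and no other vital-signs table is planned.

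The endpoint is descriptive, with no planned contrast, interval or power. The precision ratio therefore does not measure a loss against any planned analysis, and a model-based difference is optional. Within one dosed period the t-test is a valid, if inefficient, comparison of the two products, and no decision rests on it. These points also stand. They limit the importance of the finding but do not explain why a Test-versus-Reference objective should be tabled under sequence headings.

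**Conclusion.** The point holds as a mismatch between the shells and the objective. Followed as written, the plan gives no labelled or pooled product summary of vital signs. Its Total column mixes the products, and its p-values compare sequences, so the direction of any product effect reverses from period to period. A Test-Reference contrast can be decoded period by period but is not directly presented.

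The sign pattern follows from the two sequences, assuming no carryover and period-specific visit rows. The precision figures rest on assumed correlations and carry no weight in the conclusion. The consequence is confined to one secondary, descriptive safety endpoint. The bioequivalence conclusion and the adverse-event reporting by product are unaffected. The correction is worth making because it is nearly free and lets the report show the comparison that the objective states.

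**What to change.** 1. In shells 14.3.6 and 14.3.7, for the in-period timepoints (pre-dose, 2, 4, 6, 12 and 24 h), replace TRTR, RTRT and Total with Test and Reference columns, pooled over both administrations of each product.
2. State that change from baseline uses the pre-dose value of the same period.
3. Keep sequence columns for screening only.
4. Drop the independent t-test p-value from 14.3.6. A within-participant Test-Reference difference with a confidence interval is an optional replacement.
5. Add a treatment field to listing 16.2.9.4.
6. In SAP 7.2, name treatment alone as the grouping for in-period vital signs.

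**Cost:** SAP wording, two re-specified shells and one listing column. Every in-period reading already belongs to a known product through sequence and period, so no new data and no protocol amendment are needed.
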